10.5 Special Situations

Certain safety events, called ‘Special Situations’, that occur in association with study medication(s) may require reporting. These Special Situations include, but are not limited to, the following:

- Overdose of the medicinal product.
 - Darbepoetin Alfa Overdose: The PI or SmPC should be referenced for information on darbepoetin alfa overdosing.
 - Vadadustat Overdose: There is no known antidote for vadadustat. In cases of suspected overdose, Subjects should be treated per standard medical practice based on the Investigator’s judgment and dose delays and reductions may be implemented as necessary. Chronic overdosage with vadadustat may result in excessive production of red blood cells and polycythemia. Polycythemia can be potentially life threatening and may result in severe thrombosis and death (known as hyperviscosity syndrome). If hyperviscosity syndrome is observed, vadadustat should be discontinued and standard treatment for polycythemic hyperviscosity syndrome should be initiated (i.e., phlebotomy).
- Suspected abuse/misuse of the medicinal product.
- Inadvertent or accidental exposure to the medicinal product.
- Medication error involving the medicinal product (with or without subject exposure to the Sponsor’s medicinal product [eg, name confusion]).
- Drug-drug interaction.

Special situations should be reported on the Special Situations CRF whether they result in an AE/SAE or not. Special situations with associated AE/SAE should also be reported on the corresponding AE/SAE forms, following applicable AE or SAE process.

11 DATA ANALYSIS

Data collected throughout the study will be summarized using descriptive statistics and listed in by-subject listings. Continuous variables will be summarized using number of subjects with data, mean, standard deviation, median, minimum, and maximum. For categorical variables, the number and percentage of subjects in each category will be tabulated. Summaries will be

provided by treatment group within appropriate analysis populations (as defined in [Section 11.2, Study Analysis Populations](#)) and by time point/time period, as appropriate.

For Hb, Baseline will be calculated as the average of the central laboratory Hb measurements of samples taken at the screening visit closest to the date of randomization and the measurement taken at randomization.

For other parameters, unless otherwise specified, Baseline will be defined as the last available value prior to the first dose of study medication.

Hemoglobin values as assessed through the central laboratory will be used for efficacy and safety evaluations; local HemoCue Hb values will be used only for dose adjustments.

11.1 Sample Size Determination

The goal of this study is to demonstrate the efficacy and safety of vadadustat compared with darbepoetin alfa for the maintenance treatment of anemia after the correction of Hb or conversion from current ESA therapy in subjects with DD-CKD. The sample size is calculated to ensure sufficient power for testing both efficacy in this trial and the primary safety endpoints as part of a pooled analysis.

11.1.1 Sample Size for the Primary Efficacy Endpoint

The primary efficacy endpoint is defined as the mean change from Baseline in Hb (mean pretreatment Hb) to the average Hb over the primary evaluation period (mean Hb from Weeks 24 to 36, inclusive).

The primary efficacy objective of this study is to show that vadadustat is noninferior to darbepoetin alfa within the noninferiority margin. Noninferiority will be established based on a margin of -0.75 g/dL (for vadadustat minus darbepoetin alfa).

For the primary efficacy analysis in this study, it is assumed that the mean change from Baseline in Hb for vadadustat will be the same as for darbepoetin alfa, and the common standard deviation for the mean change from Baseline is assumed to be 1.5 g/dL. Noninferiority will be established based on a 2-sided 95% confidence interval (CI) for the difference between the vadadustat group and darbepoetin alfa and using a noninferiority margin of -0.75g/dL. With these assumptions and approximately 150 subjects per treatment group for the primary efficacy analysis, the noninferiority assessment will have >90% power.

11.1.2 Sample Size for the Primary Safety Endpoint

The primary safety endpoint is the time from randomization date to the first (adjudicated) MACE+ 1.

The primary safety analysis will be based upon all events that accrue over the 2 DD-CKD studies (Studies AKB-6548-CI-0016 and AKB-6548-CI-0017). The sample size with respect to the MACE endpoint has been determined based on the number of events needed to demonstrate noninferiority of the 2-sided 95% CI for the hazard ratio (vadadustat/darbepoetin alfa). It has been calculated that 631 events will be required overall to have 80% power to establish noninferiority with a margin of 1.25, and >90% power to establish noninferiority with a margin of 1.3, assuming no difference between treatment groups. The power is >90% to establish a

noninferiority margin of 1.25 if the hazard ratio is 0.95 favoring vadadustat. A MACE rate of 12% annually is anticipated in both treatment arms based on a comprehensive review of available epidemiology and prospective clinical studies in the field. The number of MACE in each study will be a function of the actual pattern and size of enrollment as well as the duration of follow-up.

11.2 Study Analysis Populations

The following analysis populations will be used in this study:

- Randomized population: defined as all randomized subjects.
- Full analysis population: defined as randomized subjects receiving 1 or more doses of study medication and had at least one Hb assessment during the primary efficacy evaluation period. This population will be analyzed based upon the randomized treatment.
- Per protocol (PP) population: defined as all randomized subjects who received study medication (vadadustat or darbepoetin alfa) during the primary evaluation period, had at least 2 Hb assessments during the primary evaluation period, received no rescue therapy (with ESA or RBC transfusion) in the 8 weeks prior to the evaluation period and have no protocol deviations affecting the primary endpoint analyses. Protocol deviations leading to exclusion from the per protocol population will be specified prior to database lock on a blinded basis and recorded in a separate document.
- Safety population: defined as all subjects who received at least 1 dose of study medication. This population will be analyzed based upon the actual treatment received.

Efficacy analyses will utilize the randomized, full analysis, and PP populations while safety analyses (including MACE) will utilize the randomized population.

11.3 Analysis of Demographic and Pretreatment Variables

Descriptive statistics will be generated for demographic and pretreatment variables for each analysis population defined in Section 11.2, Study Analysis Populations.

Medical history terms will be coded using the Medical Dictionary for Regulatory Activities (MedDRA) and summarized by System Organ Class and Preferred Term for each treatment group based on the safety population.

11.4 Disposition of Subjects

The number and percentage of subjects randomized and included in each analysis population will be summarized by treatment and overall. Reasons for excluding subjects from the analysis populations will be presented in a by-subject listing.

The number of randomized subjects who completed each period of study medication treatment (Correction/Conversion, Maintenance, and Long-term Treatment), discontinued from study medication early, and completed or discontinued from the study and reasons for discontinuation will be summarized by treatment group and overall.

11.5 Missing Data

Subjects who stop study medication treatment after randomization and prior to completion of the study should continue with planned study visits and assessments unless they withdraw consent for participation in the study. Similarly, subjects will continue with study medication and study procedures following the initiation of rescue therapy, with the exception that the subjects must discontinue taking study medication while receiving an ESA rescue therapy. Treatment with study medication should be resumed after an appropriate interval following the ESA rescue therapy as described in [Section 8.4.7, Rescue Therapy](#). Data will continue to be collected following initiation of the rescue therapy as per the study Schedule of Activities (See [Appendix A: Schedule of Activities](#)).

All data collected during the study, including at any point after the initiation of rescue therapy as well as after early discontinuation of study medication treatment, will be used for the primary analysis as well as main analyses of all efficacy endpoints. Sensitivity analyses will be performed to assess an impact of rescue therapy on study conclusions.

In the primary analysis of the primary efficacy endpoint, all available qualifying Hb measurements during the pretreatment period and during the primary evaluation period (Weeks 24 to 36) will be used to calculate an average Hb during each period respectively for each subject. For any subject with no available Hb measurements during the primary evaluation period, multiple imputation will be used to impute a change from Baseline value (details are provided in the SAP). In an analogous manner, an average Hb will be calculated for the secondary evaluation period (Weeks 40-52) for each subject. Given the design of this study where the subjects will continue to be assessed after early study medication discontinuation, it is expected that there will be only a minimal amount of missing data and the primary analysis should not be substantially affected by the imputation.

All data pertaining to the MACE endpoint collected at any point during the study, both during study medication treatment and post-study medication treatment discontinuation, and regardless of the rescue therapy, will be used for the primary analysis of the MACE endpoint and its individual components.

Unless stated otherwise in the SAP, missing data for all other secondary efficacy and safety endpoints will not be imputed and the analysis will be based on observed data. For certain responder-type binary endpoints, subjects with no available data will be classified into one of the categories as described in the relevant sections of the SAP.

11.6 Efficacy Analyses

The primary efficacy endpoint as well as all key and other secondary endpoints will be summarized using descriptive statistics by treatment group, as well as by study visit and/or analysis period as appropriate. Mean values of Hb as well as selected other efficacy parameters will be plotted across study visits/periods by treatment group.

11.6.1 Analysis of Primary Efficacy Endpoint

The primary efficacy endpoint is defined as the mean Hb change from Baseline (mean pretreatment Hb) to the mean Hb from Weeks 24 to 36 (inclusive).

11.6.1.1 Primary Analysis of Primary Efficacy Endpoint

The primary analysis will use an analysis of covariance (ANCOVA) with multiple imputation, stratified by the randomization strata and using Baseline Hb as the covariate. A 2-sided, 95% confidence interval (CI) will be calculated for the difference between treatment groups (vadadustat minus darbepoetin alfa).

Noninferiority of vadadustat will be established if the lower limit of this CI is ≥ -0.75 g/dL.

The primary analysis will be performed using the randomized population and the assigned treatment as described in [Section 11.2, Study Analysis Populations](#). All data collected during the study for subjects included in the randomized population at the time of analysis, including data collected at any point after the initiation of rescue therapy as well as after early discontinuation of study medication treatment, will be used for the primary analysis. Missing data will be handled using multiple imputation methodology as described in the SAP.

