5.3 Secondary Efficacy Endpoints

The key secondary efficacy endpoints include the following:

- Mean change in Hb value between Baseline (mean pretreatment Hb) and the secondary evaluation period (Weeks 40 to 52).
- Proportion of subjects with Hb values within the target range during the primary evaluation period (Weeks 24 to 36).
- Proportion of subjects with Hb values within the target range during the secondary evaluation period (Weeks 40-52).

Other secondary efficacy endpoints include:

- Proportion of time with Hb values within the target range during the primary evaluation period (Weeks 24-36).
- Proportion of time with Hb values within the target range during the secondary evaluation period (Weeks 40-52).
- Proportion of subjects with Hb increase of >1.0 g/dL from Baseline.
- Time to achieve Hb increase of >1.0 g/dL from Baseline.

- Mean change in Hb between Baseline (mean pretreatment Hb) and the primary evaluation period (mean Hb from Weeks 24-36) stratified by pre-Baseline ESA exposure.
- Proportion of subjects receiving RBC transfusion(s) from Baseline to Week 52.
- Proportion of subjects receiving IV iron therapy from Baseline to Week 52.
- Mean monthly dose of IV elemental iron administered from Baseline to Week 52 in subjects who have received IV iron.
- ESA rescue.
- Dose adjustments from Baseline to Week 52.

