8.5 Prior and Concomitant Therapy

8.5.1 General

All medications (except those routinely administered as part of the dialysis procedure or flushes used for routine catheter maintenance) taken during the screening period and during the study should be recorded on the appropriate CRF. If the duration of the screening period is less than 30 days, all medications taken within 30 days prior to first dose of study medication will be recorded. In addition, the ESA, blood transfusion, and iron treatment regimen prior to randomization and the date of last dose will be recorded. To ensure adequate collection of prior ESA dosing history, a minimum of 8 weeks of ESA therapy prior to start of study medication will be recorded.

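### The primary ANCOVA leaves out pre-Baseline ESA exposure, a recorded covariate on which randomization is not stratified: a small gain in precision and robustness forgone, not a validity error

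*Protocol*

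**What the plan says.** The protocol Synopsis and Section 11.6.1.1 fix the primary model as an ANCOVA with multiple imputation, "stratified by the randomization strata and using Baseline Hb as the covariate". Section 11.6.1.1 leaves the missing-data method to the SAP; it does not leave the covariate list there. Section 11.6.2.1 applies the same method to the Hb change at Weeks 40 to 52.

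Sections 5.1 and 6.1 describe a mixed population: subjects treated after correction of Hb, and subjects converted from current ESA therapy. Section 8.4.2 stratifies randomization by region, NYHA class and study entry Hb, and by nothing else.

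Prior ESA use is on record. Section 8.5.1 collects the ESA regimen before randomization and the date of last dose, and adds that "a minimum of 8 weeks of ESA therapy prior to start of study medication will be recorded". Section 5.3 lists, among the other secondary endpoints, the Hb change to Weeks 24 to 36 "stratified by pre-Baseline ESA exposure". The factor is absent from the sensitivity analyses in Section 11.6.1.2 and from the subgroups in Section 11.6.3.

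**The concern.** The same Baseline Hb can mean different things in the two kinds of subject. Baseline is the average of the last screening value and the randomization value (Section 11). ESA is permitted during Screening and only discouraged after the second screening visit (Section 8.5.2), so a value of, say, 9.5 g/dL may be ESA-supported in one subject and untreated in another. If their later Hb changes differ, part of that difference stays in the residual error, and any chance imbalance in ESA use between arms goes straight into the treatment estimate. Randomization does not control that imbalance directly.

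The protocol treats prior ESA use as relevant. It is a reason to postpone the first dose (Section 8.4.4), it sets the starting regimen for earlier darbepoetin users in the control arm (Section 8.4.4.2), and it defines a secondary endpoint.

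At stake are the width of the noninferiority interval and protection against a dispute after the fact should the arms turn out unbalanced. A secondary result split by ESA exposure describes the heterogeneity but does not adjust the confirmatory estimate.

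**Working it through.** **Inputs from Section 11.1.1.** Margin -0.75 g/dL with a two-sided 95% interval; "the common standard deviation for the mean change from Baseline is assumed to be 1.5 g/dL"; true difference zero ("it is assumed that the mean change from Baseline in Hb for vadadustat will be the same as for darbepoetin alfa"); "approximately 150 subjects per treatment group for the primary efficacy analysis, the noninferiority assessment will have >90% power".

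**Inputs not in the documents (assumed).** Share of subjects with prior ESA, p = 0.5. Difference in mean change between exposed and unexposed subjects that remains after Baseline Hb and strata, d = 0.5 to 1.0 g/dL. The planning SD of 1.5 is used as the SD before the term is added, since no covariate-adjusted SD is given.

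**1. Reproduce the stated power.**
- SE = 1.5 × √(2/150) = 0.173 g/dL; half-width = 1.96 × 0.173 = 0.339 g/dL.
- Power = Φ(0.75/0.1732 − 1.96) = Φ(2.37) = 99.1%, consistent with the stated figure. About 85 per arm would give 90%.

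**2. Effect of adding the term.** R² = d² p(1−p)/1.5², and the SE is multiplied by √(1−R²). Power at a true difference δ is Φ((0.75 − |δ|)/SE − 1.96).

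| d (g/dL) | R² | SE | Half-width | Narrowing | Power, δ = 0 | Power, δ = −0.25 |
|---|---|---|---|---|---|---|
| no term | 0 | 0.173 | 0.339 | – | 99.1% | 82.3% |
| 0.5 | 0.25 × 0.25/2.25 = 0.028 | 0.171 | 0.335 | 1.4% | 99.2% | 83.3% |
| 1.0 | 1 × 0.25/2.25 = 0.111 | 0.163 | 0.320 | 5.7% | 99.6% | 86.5% |

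**3. Chance imbalance.**
- SD of the between-arm difference in share exposed = √(2 × 0.25/150) = 0.058.
- Imbalance exceeded in 1 trial in 20 (either direction) = 1.96 × 0.058 = 0.113, about 11 percentage points.
- Shift in the unadjusted estimate = 0.113 × d = 0.057 g/dL (d = 0.5) to 0.113 g/dL (d = 1.0). That is 0.33 to 0.65 of the SE, or 8% to 15% of the margin.
- With 30% or 70% exposed, the shift is 0.052 to 0.104 g/dL. If ESA use is associated with region or entry Hb, stratified randomization would balance part of it and the shift would be smaller.

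**4. Validity.** Simulation at the margin (20,000 trials, 150 per arm, half exposed) gave a one-sided type I error of 0.0247 without the term and 0.0236 with it for d = 0.5, and 0.0254 and 0.0252 for d = 1.0. All are near the nominal 0.025.

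**The case against.** The case against is substantial, and most of it stands.

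*The model was reopened.* A reader might infer that the population widened while the analysis stayed fixed. The amendment history in Appendix E does not support that. Amendments 2 and 3 admitted subjects on ESA, and Amendment 4 then replaced the analysis with an ANCOVA using Baseline Hb and multiple imputation. What can be said is narrower: at that revision the ESA term was not added.

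*Baseline Hb may absorb much of the difference.* Within each region both arms are titrated to the same target, the endpoint falls at Weeks 24 to 36, and subjects meeting the ESA-resistance criteria are excluded (exclusion criterion 19). Change is then largely target minus baseline. The documents give no Hb course by ESA history, so it cannot be stated as fact that Baseline Hb falls short. The assumed 0.5 to 1.0 g/dL must be read as what remains after adjustment, and it could be smaller.

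*The interval already allows for chance imbalance.* This is correct, and it is why the omission is not an error. Adjustment protects the estimate conditional on the imbalance actually seen.

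*ESA exposure is already examined.* It is, through the other secondary endpoint, but outside the primary model.

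*Imputation.* A reader might infer that the imputation model also ignores ESA history. Its content is left to the SAP, so nothing can be concluded.

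**Conclusion.** The point holds as a small, nearly free improvement. The primary ANCOVA omits a recorded baseline variable that the protocol itself treats as relevant and does not balance by stratification. The gain is an interval about 1% to 6% narrower and removal of a possible shift of about 0.06 to 0.11 g/dL. Both rest on assumed prevalence and effect, and both shrink if Baseline Hb and the common target absorb most of the difference.

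A reader might go further and call the test invalid, the estimate biased or the sample size wrong. None of these follows. Randomization keeps the unadjusted comparison unbiased, type I error is held, and planned power is well above the stated 90%. The power gain matters only if vadadustat is truly somewhat worse: at −0.25 g/dL, 82.3% would become about 83% to 86%.

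**What to change.** Add one binary covariate, any ESA in the 8 weeks before randomization, to the primary ANCOVA in Section 11.6.1.1 and to the key secondary Hb-change ANCOVA in Section 11.6.2.1. Keep the analysis stratified by ESA exposure as supportive.

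The window must end at randomization, not at first dose. Sections 8.4.4 to 8.4.4.2 let the investigator postpone the first dose after open-label randomization, so a window ending at first dose could take in post-randomization time. It would also be undefined for any randomized subject never dosed, and the primary analysis covers all randomized subjects.

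The cost is one model term, negligible in degrees of freedom with about 300 subjects. No new data item is needed, because Section 8.5.1 already records the ESA regimen before randomization and the date of last dose. Its 8-week minimum is counted back from first study dose, however, so the derivation should be specified from randomization. The definition should be fixed before treatment-group results are seen.

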11.6.1.2 Sensitivity Analyses of Primary Efficacy Endpoint

The following sensitivity analyses will be conducted:

- Primary analysis will be repeated using the full analysis population.
- Primary analysis will be repeated using only subjects with available Hb data during the primary evaluation period, ie, excluding subjects with no available data during the primary evaluation period.
- Primary analysis will be repeated using the PP population with the actual treatment received.
- Primary analysis will be repeated with alternate approaches to imputation of missing data as described in the SAP.
- Primary analysis will be repeated with imputation of data which may have been affected by a subject's having received any form of rescue (transfusion or ESA). Details are provided in the SAP.

11.6.2 Secondary Efficacy Analyses

Secondary efficacy endpoints analyses will be performed using the randomized and full analysis populations and the assigned treatment as described in [Section 11.2, Study Analysis Populations](#). Analysis for the key secondary efficacy endpoints will be repeated using the PP population with the actual treatment received.

11.6.2.1 Key Secondary Efficacy Analyses

Mean change in Hb value between Baseline and the secondary evaluation period (Weeks 40-52) will be analyzed using the same methodology as specified for the primary efficacy endpoint. Sensitivity analyses similar to those of the primary efficacy endpoint will be performed and details will be provided in the SAP.

11.6.3 Subgroups

Analyses of the primary efficacy endpoint and key secondary efficacy endpoints will also be performed using the randomized and full analysis populations, using the assigned treatment, for subgroups based on the following:

- Hb stratification level.
- NYHA CHF stratification level.
- Due to use of different target Hb levels in the US vs. the non-US, the endpoints will also be analyzed for subsets based on the target Hb level:
 - The US subset will be assessed due to the target Hb range being 10.0-11.0 g/dL in the US.
 - The combined EU and ROW (non-US) subset will be assessed since the target Hb range is 10.0-12.0 g/dL in these two Regions.
- Geographic region (US, EU, ROW).
- Age.
- Gender.
- Race.

